3.2. Disposition Information

The distribution of the number of subjects who are randomized, receive double-blind treatment, and complete the Week 12 will be presented by treatment group for the doubleblind phase of the study. In addition, the distribution of trial termination reasons will be summarized. These summaries will include a total group. The All Randomized Subjects analysis set will be used to summarize this information. A subject will be considered to have completed the Week 12 treatment phase if he or she has completed assessments through Week 12 visit.

3.3. Extent of Exposure

Total duration of exposure during the DB phase is defined as days between the first and the last dose of DB study medication.

Descriptive statistics (N, mean, median, and range) of total duration of exposure will be presented for DB phase by treatment group in safety analysis set. A frequency distribution showing the number of doses received during the double-blind phase will also be provided.

3.4. Protocol Deviations

Deviations that occurred during the study will be listed.

3.5. Prior and Concomitant Medications

The number and percent of subjects who receive concomitant therapies will be summarized by planned treatment group and by the generic term of the medication for the safety analysis set. Concomitant medications will be summarized in DB and FU separately.

A similar summary will be presented for antidepressants received prior to study entry according to responses to the MGH-ATRQ for the Safety analysis set.

4. EFFICACY

Efficacy data will be provided for the interim efficacy analysis; however, they will not be provided for the first DMC Safety Review meeting, except for Item 3 (Suicide) of HDRS₁₇ and Item 18 (Suicide Ideation) of IDS-C30 which will be provided for DMC Safety Review meetings.

The efficacy variables in this study are listed in Table 4.

Table 4: Efficacy Variables	
Scale	End point
Change in HDRS ₁₇ total score from baseline to Week 12	Primary
Change in HDRS ₁₇ total score from baseline to Weeks 1, 4, 8, 16 or 22	Secondary
Response rate (\geq 50% improvement in HDRS ₁₇ total score from baseline) at Week 12	
Remission rates (HDRS ₁₇ total score \leq 7) at Week 12	
Change in CGI-S score from baseline to Weeks 1, 4, 8, 12, 16 and 22	
Change in SHAPS total score from baseline to Weeks 1, 4, 8, 12, 16 and 22	
Change in FACIT Fatigue total score from baseline to Weeks 1, 4, 8, 12, 16 and 22	
Change in IDS-C30 from baseline to Weeks 1, 4, 8, 12, 16 and 22	Exploratory
Change in PHQ-9 total score from baseline to Weeks 1, 4, 8, 12, 16 and 22	

4.1. Analysis Specifications

4.1.1. Level of Significance

Unless otherwise specified, all statistical comparisons will be carried out at a 1-sided significance level of 12.5% and confidence intervals will be presented at 2-sided confidence level of 75% (ie. equivalent to 1-sided confidence level of 87.5%).

4.1.2. Data Handling Rules

The last observation carried forward (LOCF) method will be applied to the $HDRS_{17}$ total score in the sensitivity analysis.

The LOCF approach will be used for imputing missing visit data in the ITT LOCF sensitivity efficacy analyses. The LOCF calculation will be performed for all scheduled post-baseline time windows in the double-blind phase.

4.1.3. Imputation Methods for Missing Items

Imputation of missing individual item scores will apply only to the $HDRS_{17}$, as described in the next section. For all other scales where multiple items are summed to create a total, if any item of the scale is missing on one visit, the total score for that scale at that visit will be left blank.

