4.2. Primary Efficacy Endpoint

4.2.1. Definition

The HDRS₁₇ is a clinician-administered rating scale designed to assess the severity of symptoms in subjects diagnosed with depression with a score range of 0 to 52. Each of the 17 items is rated by the clinician on either a 3- or a 5-point scale. The HDRS₁₇ consists of 17 items that cover all of the core depressive symptoms (depressed mood, feeling of guilt, suicide, insomnia early, insomnia middle, insomnia late, work and activities, retardation [psychomotor], agitation, anxiety [psychological], anxiety somatic, somatic symptoms general, genital symptoms, hypochondriasis, loss of weight and insight). A total score (0 to 52) is calculated by adding the scores of all 17 items. For each item as well as the total score, a higher score represents a more severe condition. If 2 or more items are missing, no imputation will be performed and the total score will be left missing. Otherwise, the total score will be calculated as the sum of the items present multiplied by the ratio of the maximum possible number of items (i.e., 17) to the number of items present.

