4.2.6. Patient Health Questionnaire (PHQ-9)

The PHQ-9 is used as a subject-reported measure of depressive symptomatology. The PHQ-9 is a 9-item scale, where each item is rated on a 4-point scale (0=Not at all, 1=Several Days, 2=More than half the days, and 3=Nearly every day), with a total score range of 0 to 27. The recall period is 2 weeks.

Descriptive statistics (N, mean, median and range) of total score and as well changes from baseline will be provided by treatment group.

In addition, analyses on changes from baseline in PHQ-9 total score may also be conducted using the similar aforementioned MMRM for the primary analyses.

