4.2.7. Snaith–Hamilton Pleasure Scale (SHAPS)

Anhedonia, the inability to experience pleasure, is a core symptom of depression. The Snaith–Hamilton Pleasure Scale (SHAPS) is a short, 14-item instrument to measure anhedonia, which has been shown to be valid and reliable in normal and clinical samples. Each of the 14 items has a set of four response categories: Definitely Agree, Agree, Disagree, and Definitely Disagree.

There will be two definitions for total score. The (protocol) definition 1: Definitely Agree (=1), Agree (=2), Disagree (=3), and Definitely Disagree (=4). The definition 2: Definitely Agree (=0), Agree (=0), Disagree (=1), and Definitely Disagree (=1). A SHAPS total score will be calculated as the sum of the 14 item scores. A higher total score indicates higher levels of state anhedonia.

Descriptive statistics (N, mean, median and range) of total score (for both definitions) and as well changes from baseline will be provided by treatment group.

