4.2.8. Functional Assessment of Chronic Illness Therapy-Fatigue (FACIT Fatigue)

The FACIT-Fatigue is a questionnaire that assesses self-reported tiredness, weakness, and difficulty conducting usual activities due to fatigue. The subscale consists 13-item instrument to measure fatigue. Each of the 13 items has a set of five response categories: Not at all (=0), A little bit (=1), Somewhat (=2), Quite a bit (=3) and Very much (=4). A total FACIT-Fatigue subscale score will be calculated as the sum of the 13 item scores (reserved scores [4 – score] for all except for 2 items: "I have energy" and "I am able to do my usual activities"), and ranges from 0 to 52, with a higher score indicating less fatigue.

Descriptive statistics (N, mean, median and range) of total score and as well changes from baseline will be provided by treatment group.

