4.3.2. Childhood Trauma Questionnaire (CTQ)

The self-report includes a 28-item test that measures 5 types of maltreatment – emotional, physical, and sexual abuse, and emotional and physical neglect. A 5-point Likert scale is used for the responses which range from Never True to Very Often True. A total CTQ score will be calculated as the sum of the 28 item scores (reserved scores for items 2, 5, 7, 10, 13, 16, 19, 22, 26 and 28), and ranges from 28 to 140, with a higher score indicating a more server childhood trauma.

Physical abuse is 'yes' if sum of CTQ items 9, 11, 12, 15, 17 is 8 or larger. Physical neglect is 'yes' if sum of CTQ items 1, 2 (R) (where R stands for reserving score), 4, 6, 26 (R) is 8 or larger. Sexual abuse is 'yes' if sum of CTQ items 20, 21, 23, 24, 27 is 8 or larger. Emotional abuse is 'yes' if sum of CTQ items 3, 8, 14, 18, 25 is 10 or larger. Emotional neglect is 'yes' if sum of CTQ items 5 (R), 7 (R), 13 (R), 19 (R), 28 (R) is 15 or larger.

Descriptive statistics (N, mean, standard deviation, median and range) of the numerical total scores may be provided by treatment. A frequency distribution of CTQ will be provided by treatment group. Frequency distributions of physical abuse, physical neglect, sexual abuse, emotional abuse and emotional neglect will also be provided by treatment group.

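### One missing item blanks the whole PHQ-9, SHAPS or FACIT-Fatigue total, although the SAP prorates one missing item on the HDRS17; extending that rule is a cheap improvement

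*SAP*

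**What the plan says.** Section 4.1.3 restricts item-level imputation to one scale: "Imputation of missing individual item scores will apply only to the" HDRS17. For the other summed scales, "if any item of the scale is missing on one visit, the total score for that scale at that visit will be left blank".

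For the HDRS17, Section 4.2.1 scales the sum up by 17 over the number of items present when one item is missing, and stops there: "If 2 or more items are missing, no imputation will be performed and the total score will be left missing". The same section describes the items as unequal in range: "Each of the 17 items is rated by the clinician on either a 3- or a 5-point scale".

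The three self-report scales have uniform items:

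- PHQ-9 (Section 4.2.6): "The PHQ-9 is a 9-item scale, where each item is rated on a 4-point scale", scored 0 to 3.
- SHAPS (Section 4.2.7): "Each of the 14 items has a set of four response categories", summed under two scoring definitions.
- FACIT-Fatigue (Section 4.2.8): five categories scored 0 to 4; the total "will be calculated as the sum of the 13 item scores", with all but two items reversed.

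All three are summarised as change from baseline. Section 4.1.2 states LOCF for the HDRS17 total in a sensitivity analysis. No stated rule restores a blank total on the other scales.

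**The concern.** The SAP accepts one-item proration on a scale whose items differ in range, but not on three scales whose items share a range. It gives no reason for the difference. One unanswered question then discards 8 of 9, 12 of 13 or 13 of 14 valid answers.

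The consequence depends on when the item is missed. After baseline, only that scale's total at that visit goes; other visits and other scales remain. At baseline, every change score on that scale goes for that subject, unless an earlier pre-dose form supplies a total (Section 2.4 takes the last observation before the first dose). A repeated-measures model of change cannot recover such a subject.

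SHAPS, PHQ-9 and FACIT-Fatigue are the named measures for secondary objectives 2, 5 and 6 in Section 1.1. What is at stake is precision on those outcomes.

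**Working it through.** **The plan's own figures.** The item rule carries none. The design figure in Section 1.4 does reproduce: 48 per arm for a difference of 4, SD 8, one-sided 0.125 and 90% power; 96 / 0.75 = 128; 128 / 0.90 = 142.2, against 142 stated. Nothing below depends on it.

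**Inputs.** Number of items k: PHQ-9 9, FACIT-Fatigue 13, SHAPS 14 (Sections 4.2.6 to 4.2.8). Per-item missing rate q: not in the SAP; assumed 0.1% to 1%, independent across items and visits.

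**Step 1: loss under the current rule.**

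- One total is blank with probability 1 − (1 − q)^k.
- A baseline-to-Week 12 change needs two complete forms, so it is lost with probability 1 − (1 − q)^(2k). For example, PHQ-9 at 1%: 1 − 0.99^18 = 16.5%.

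| Scale | Total blank at q = 0.1 / 0.5 / 1% | Change lost at q = 0.1 / 0.5 / 1% |
|---|---|---|
| PHQ-9 | 0.9 / 4.4 / 8.6% | 1.8 / 8.6 / 16.5% |
| FACIT-Fatigue | 1.3 / 6.3 / 12.2% | 2.6 / 12.2 / 23.0% |
| SHAPS | 1.4 / 6.8 / 13.1% | 2.8 / 13.1 / 24.5% |

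**Step 2: loss if the HDRS17 one-item rule were extended.** A total is then blank only if two or more items are missing. At q = 1% this is 0.3% (PHQ-9), 0.7% (FACIT-Fatigue) and 0.8% (SHAPS). Lost change scores fall to 0.7%, 1.4% and 1.7%.

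**Step 3: effect on precision.** Losing a fraction L of change scores widens a standard error by a factor 1/√(1 − L). For SHAPS this is 1/√(1 − 0.0276) = 1.01 at q = 0.1% and 1/√(1 − 0.2453) = 1.15 at q = 1%. For PHQ-9 at 1% it is 1/√(1 − 0.1655) = 1.09.

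**Step 4: error introduced by proration.** Assume equal item variances and a common inter-item correlation r of 0.3 to 0.5 (not in the SAP). For one missing item:

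- SD of the error relative to the SD of the full total = √{(1 − r) / [(k − 1)(1 + (k − 1)r)]}.
- PHQ-9, r = 0.3: √(0.7 / (8 × 3.4)) = 0.16. SHAPS, r = 0.5: √(0.5 / (13 × 7.5)) = 0.07. FACIT-Fatigue lies between, at 0.08 to 0.11.
- Correlation of prorated and full totals = √{(k − 1)(1 + (k − 1)r) / [k(1 + (k − 2)r)]}. PHQ-9, r = 0.3: √(27.2 / 27.9) = 0.987, the lowest of the three scales. SHAPS, r = 0.5: √(97.5 / 98) = 0.997, the highest.

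**The case against.** The strongest reply is that this is not an error. Section 4.1.3 states one clear, prespecified rule, and complete-item scoring of supportive scales is a defensible conservative choice. That stands: a reader might infer a contradiction between Sections 4.1.3 and 4.2.1, but 4.1.3 names the HDRS17 as the exception and 4.2.1 carries it out. What remains is an unexplained difference in treatment.

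The size is also assumed. The SAP does not say how often items are missed, or whether data capture allows skipping. At 0.1% per item the loss is 2-3%, and clustering in a few subjects would reduce the figures further. This stands too, and is why a range is shown.

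Little inference is affected. The sections on SHAPS and FACIT-Fatigue plan descriptive statistics only, Table 4 appears to group PHQ-9 with the exploratory variables, and MMRM on these scales is optional. This limits severity, but does not argue against a few lines of text.

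Four stronger readings are tempting but not supported:

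- **Affected subjects leave the analysis altogether.** After baseline they lose one total at one visit. Only a blank baseline removes their change scores, and only on that scale.
- **Proration would cure bias.** If an item is skipped for a reason, replacing it by the mean of the others assumes that reason away.
- **The CTQ should be included.** Section 4.3.2 says "A total CTQ score will be calculated as the sum of the 28 item scores", so a blank total is possible. But no CTQ change score is planned, Table 1 has no CTQ window, and the five maltreatment flags use their own five-item sums. The total spans five types of maltreatment; a rule accepting 23 of 28 answers could fill in a whole five-item domain from unrelated ones.
- **These are the scales where proration works best.** The document does not say so. A common range makes proration natural; it does not make item means equal.

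**Conclusion.** The point holds as a cheap improvement of low severity. For PHQ-9, SHAPS and FACIT-Fatigue, the SAP gives up whole totals for one missing item while allowing one missing item on the HDRS17, and no other stated rule recovers them.

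The size rests on an item-missing rate that the documents do not give and on independence between items and visits. It ranges from negligible, at 0.1% per item, to a loss of up to about a quarter of SHAPS change scores at 1%. Nearly all of that loss is recoverable with the sponsor's own one-item rule. The benefit is confined to precision on supportive secondary and exploratory outcomes. The primary analysis is unaffected.

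**What to change.** In Section 4.1.3, extend the one-item rule of Section 4.2.1 to PHQ-9, SHAPS (both scoring definitions) and FACIT-Fatigue:

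- If exactly one item is missing, total = (sum of answered items, after reversal where it applies) × (number of items) / (number answered).
- If two or more items are missing, leave the total blank.
- Report the number of prorated forms by treatment group and visit.

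Leave the CTQ total as it is, and keep the IDS-C30 item-pair rule of Section 4.3.1, which already governs the items not meant to be rated. If the sponsor prefers complete-item scoring, one sentence giving the reason would suffice.

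The cost is a few lines of SAP text and programming, best settled before unblinding. The downside is a small scoring error in prorated totals: about 7-16% of the total's SD for one missing item, under the inter-item correlations assumed above.

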4.2. Primary Efficacy Endpoint

4.2.1. Definition

The HDRS₁₇ is a clinician-administered rating scale designed to assess the severity of symptoms in subjects diagnosed with depression with a score range of 0 to 52. Each of the 17 items is rated by the clinician on either a 3- or a 5-point scale. The HDRS₁₇ consists of 17 items that cover all of the core depressive symptoms (depressed mood, feeling of guilt, suicide, insomnia early, insomnia middle, insomnia late, work and activities, retardation [psychomotor], agitation, anxiety [psychological], anxiety somatic, somatic symptoms general, genital symptoms, hypochondriasis, loss of weight and insight). A total score (0 to 52) is calculated by adding the scores of all 17 items. For each item as well as the total score, a higher score represents a more severe condition. If 2 or more items are missing, no imputation will be performed and the total score will be left missing. Otherwise, the total score will be calculated as the sum of the items present multiplied by the ratio of the maximum possible number of items (i.e., 17) to the number of items present.

4.2.2. Analysis Methods

The primary efficacy analyses will be conducted using mITT1 analysis set. The primary comparison will be between sirukumab and placebo using the primary efficacy endpoint, i.e., change in HDRS₁₇ total score from baseline to Week 12.

A mixed effects model using repeated measures (MMRM) with time, treatment, country, screening hsCRP stratification and time-by-treatment interaction as factors, baseline HDRS₁₇ total score as a continuous covariate, and a random subject effect, will be conducted. An unstructured variance-covariance matrix will be used (if there are convergence issues with the unstructured variance-covariance matrix, another suitable matrix structure will be chosen based on the LR test or the AIC). The contrast on Week 12 changes will be of primary interest, and tested at one-sided alpha level of 0.125. Descriptive statistics for values and changes from baseline will be provided for HDRS₁₇ including individual items and total score, at each time point of the double-blind treatment phase. Time profile of HDRS₁₇ total score for individual subjects will be represented graphically over time by treatment group.

Sensitivity analyses on the primary endpoint will also be conducted. Sensitivity analyses will be using the aforementioned MMRM using mITT3 and mITT2 analysis sets.

The primary endpoint with the aforementioned MMRM analyses may also be explored in subgroups such as 5 types of maltreatment based on CTQ (physical abuse, physical neglect, sexual abuse, emotional abuse and emotional neglect) and baseline BMI status (≤ 25 (normal) vs. >25 (abnormal) or ≤ 30 (normal) vs. >30 (abnormal)).

In addition, the primary endpoint using similar MMRM analyses with additional covariates such as CTQ total score or others may also be explored.

Secondary Efficacy Endpoints

Analyses of secondary efficacy endpoints will be mainly based on the mITT2 analysis set. Analyses on the secondary efficacy endpoints may also be conducted using the aforementioned MMRM using mITT1 and mITT3 analysis sets.

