1.4. Sample Size Justification

Approximately 192 subjects will be enrolled in this study, with approximately 96 subjects randomized per treatment group.

The target study population is male and female subjects with MDD who have had a suboptimal response to standard oral antidepressant therapy; have failed no more than 3 antidepressant treatments in the current major depressive episode; approximately 142 subjects with screening hsCRP $\geq 0.300 \text{ mg/dL}$ (SI 3.00 mg/L) and approximately 50 subjects with screening hsCRP<0.300 mg/dL (SI 3.00 mg/L) will be enrolled.

The expected final sample size of 142 for subjects with screening hsCRP ≥ 0.300 mg/dL (SI 3.00 mg/L) was determined based on the assumption of an effect size of at least 0.5 for the HDRS17 (mean change from baseline to week 12 endpoint between the sirukumab and placebo groups of 4 with SD=8). This is considered to be a clinically relevant difference in a population with suboptimal response to standard oral antidepressant therapy. Power is set at 90.0%, with a 1-sided alpha of 0.125 and a 12-week drop-out rate of 25%. It was also assumed that 10% of the randomized subjects would be excluded from the primary efficacy analysis due to having hsCRP ≥ 3.00 mg/L at screening but not at baseline.

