4.2.3. HDRS₁₇ Total Score

Changes in HDRS₁₇ from baseline to Weeks 1, 4, and 8 will be analyzed using the same mixed-effects model with repeated measures (MMRM) as for the primary endpoint in all 3 mITT analysis datasets.

Summary statistics on HDRS₁₇ (changes from baseline) over time by treatment group will be provided for the following subgroups: (1) Screening hsCRP stratification;

(2) TRD status (TRD vs. non-TRD);

Other subgroups such as 5 types of maltreatment (physical abuse, physical neglect, sexual abuse, emotional abuse and emotional neglect) based on CTQ and baseline BMI status (\leq 25 (normal) vs. >25 (abnormal) or \leq 30 (normal) vs. >30 (abnormal)) may also be explored.

In addition, mean time profile plots of $HDRS_{17}$ over time by treatment group will be provided.

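### The primary MMRM fixes one baseline HDRS17 slope for all visits; adding baseline-by-time is a cheap safeguard for the Week 12 contrast, not the repair of an invalid model

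*SAP*

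**What the plan says.** SAP 4.2.2 specifies an MMRM with time, treatment, country, "screening hsCRP stratification and time-by-treatment interaction as factors". Baseline HDRS17 enters once: "total score as a continuous covariate, and a random subject effect, will be conducted". For the residuals, "An unstructured variance-covariance matrix will be used", with a fallback structure if the fit does not converge. The decision rests on one visit: "The contrast on Week 12 changes will be of primary interest, and tested at one-sided alpha level of 0.125".

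No baseline-by-time term is listed there or elsewhere. The sensitivity analyses in 4.2.2 rerun the same model in mITT3 and mITT2. Section 4.2.3 uses it for the earlier visits: changes "from baseline to Weeks 1, 4, and 8 will be analyzed using the same mixed-effects model". Models with further covariates are allowed in 4.2.2, but they are optional and this interaction is not named. The LOCF analysis in 4.1.2 changes how missing data are handled and does not test the common slope within the MMRM.

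Section 1.4 bases the sample size on a "mean change from baseline to week 12 endpoint between the sirukumab and placebo groups of 4 with SD=8" and adds: "Power is set at 90.0%, with a 1-sided alpha of 0.125 and a 12-week drop-out rate of 25" per cent.

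**The concern.** The slope of change on baseline at visit t is Cov(Y_t, Y_0)/Var(Y_0) − 1. A common slope requires the covariance of the score with baseline to be the same at Day 7 as at Day 84. The model lets the treatment effect, variances and covariances vary by visit, yet holds its one continuous prognostic covariate constant. If the slopes differ, the baseline adjustment at Week 12 is partly borrowed from earlier visits.

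Two things are then at stake. Baseline variation left unexplained at Week 12 inflates the standard error. Dropout can also turn the wrong slope into bias. Roughly, the bias is (Week 12 slope − common slope) × (between-arm difference in mean baseline among those still observed at Week 12), tempered by what earlier visits tell about the missing values. If either factor is zero, there is no bias.

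**Working it through.** **The plan's own figure.** With difference 4, SD 8, one-sided alpha 0.125 and power 90% (SAP 1.4), n per arm = 2 × (1.1503 + 1.2816)² × (8/4)² = 47.3, so 48 per arm and 96 in total. Power at 48 per arm is 90.3%. Then 96/(1 − 0.25) = 128, and 128/(1 − 0.10) = 142.2, against 142 stated. The formula uses the raw SD with no baseline adjustment, so the number does not depend on the baseline term.

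**First set of simulations.** From the SAP: four post-baseline visits, true difference 4, Week 12 SD 8, 128 subjects (64 per arm), about 25% dropout. Assumed: baseline SD 4.5; residual correlation 0.65^lag; slopes at Weeks 1/4/8/12 of −0.4 throughout (equal), −0.15/−0.3/−0.4/−0.5 (moderate) or −0.1/−0.4/−0.7/−1.0 (strong). There were 700 runs per setting, with unstructured covariance. Country, hsCRP stratum and the separate random subject effect were left out. Each cell gives one slope / visit-specific slopes. Positive bias means that the benefit is understated; its Monte Carlo error is about 0.06.

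| Slopes | Dropout | Model SE | Bias | Power % |
|---|---|---|---|---|
| Equal | none | 1.370 / 1.374 | −0.06 / −0.07 | 96.3 / 96.0 |
| Equal | random | 1.543 / 1.550 | 0.03 / 0.03 | 94.1 / 93.9 |
| Equal | opposite by arm | 1.543 / 1.575 | 0.01 / 0.02 | 92.1 / 91.1 |
| Moderate | random | 1.553 / 1.538 | −0.06 / −0.07 | 92.7 / 93.4 |
| Moderate | response-driven | 1.539 / 1.523 | −0.05 / −0.06 | 92.4 / 92.6 |
| Moderate | baseline, same in both arms | 1.554 / 1.540 | 0.01 / 0.01 | 93.1 / 93.4 |
| Moderate | opposite by arm | 1.541 / 1.551 | 0.45 / 0.04 | 87.9 / 90.4 |
| Strong | random | 1.464 / 1.323 | 0.03 / 0.03 | 95.3 / 97.6 |
| Strong | response-driven | 1.444 / 1.310 | 0.00 / −0.03 | 92.9 / 96.7 |
| Strong | baseline, same in both arms | 1.452 / 1.322 | −0.04 / −0.02 | 93.9 / 96.4 |
| Strong | opposite by arm | 1.447 / 1.335 | 0.97 / −0.07 | 81.7 / 96.4 |

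Here 'opposite by arm' means that dropout depends on baseline in opposite directions in the two arms.

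- Cost with equal slopes: 1.374/1.370 = 1.003 and 1.550/1.543 = 1.005; with opposite-direction dropout, 1.575/1.543 = 1.021.
- Penalty for the single slope under random dropout: 1.553/1.538 = 1.010 (moderate) and 1.464/1.323 = 1.107 (strong).
- One-sided type I error under random or response-driven dropout was 0.10 to 0.14 for both models (nominal 0.125). With moderate slopes and opposite-direction dropout it was 0.057 for the single slope and 0.110 with the interaction. By symmetry, mirroring the dropout pattern reverses the sign of the bias.

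**Second set, other assumptions.** 128 subjects, about 25% dropout, baseline SD 4, visit SDs 5, 6, 7 and 8, correlation 0.75 per visit step. With slopes running from −0.10 to −0.50, the interaction lowered the Week 12 variance by 2 to 3%, which is 1 to 1.5% of the SE. From −0.05 to −0.70 it lowered the variance by 8%, and 1 − √0.92 = 4% of the SE.

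The gap between the two models in the Week 12 estimate depends on how far dropout differs by arm (moderate slopes, 400 runs each):

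| Log-odds of dropout per baseline point, by arm | Gap (points) |
|---|---|
| +0.1 / −0.1 | 0.27 |
| +0.1 / 0 | 0.15 |
| +0.1 / +0.05 | 0.09 |
| equal in both arms | 0.03 |

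The standard error is near 1.55 in all four. At +0.25/−0.25 the single-slope estimate of a true 4.0 was 3.4, or 2.9 with the steeper slopes: 0.6 and 1.1 points too small.

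**The case against.** The strongest objection is that this is a modelling preference. The specification is complete, contradicts nothing in the SAP, and keeps its type I error under ordinary dropout. That stands: a reader might infer that the primary analysis is invalid or biased as planned, and neither the SAP nor the simulations support this.

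The SAP gives no baseline SD, visit-specific slopes or correlations, so the size of any loss is assumed. That the slope steepens with follow-up is a reasonable expectation, but no section of the SAP shows it. With moderate slopes the power difference, 92.7% against 93.4%, is within simulation error. This also stands.

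Bias needs unequal slopes and arm-specific, baseline-related dropout together, and the largest values come from severe patterns. A log-odds of 0.25 per point over two SDs (8 points) is an odds ratio of exp(2) = 7.4, in opposite directions by arm. Nothing in the SAP points to that.

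A reader might also infer that the extra term is free. It is not: with equal slopes it gains nothing and widens the standard error slightly. In a 40-subject run with equal slopes the empirical SD rose from 2.89 to 2.95, about 2%. That argues against carrying the term automatically into the CTQ and BMI subgroup models, since the SAP already provides for convergence problems in the full model.

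What the objection does not remove is the imbalance of the trade. The term costs about 0.5% of the standard error, or about 2% at worst, and guards against a loss of up to about 10% and a bias that nothing else in the plan is designed to reveal.

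**Conclusion.** A minor but worthwhile improvement. The primary model imposes one baseline slope on four visits, and no committed analysis relaxes it. If the slopes are equal, nothing is lost. If they differ, the Week 12 standard error is about 1% (moderate) to about 10% (strong) larger than it need be. If dropout also depends on baseline differently by arm, the estimate moves by about 0.1 to 0.5 points on a true 4 with moderate slopes, and by about 1 in extreme settings. The direction depends on the dropout pattern, so the error could favour either arm.

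These sizes rest on assumed slopes, baseline SD and correlations, and on simulated models without country, hsCRP stratum and the separate random subject effect. The 142 in SAP 1.4 reproduces and stands.

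**What to change.** Before unblinding, add a baseline HDRS17-by-time interaction to the primary MMRM in SAP 4.2.2. It then carries over to the mITT2 and mITT3 reruns and to the Week 1, 4 and 8 HDRS17 analyses in 4.2.3. State that the term is optional in the small exploratory subgroup models. If the sponsor prefers to keep the primary model as written, the minimum is to prespecify the interaction model as a named sensitivity analysis.

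The cost is one line of text and three parameters (four visits less one). The standard error rises by about 0.3 to 0.5% if the slopes are truly equal, or about 2% if baseline-related dropout also runs in opposite directions by arm. The sample size does not change.
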